9.1.1. Inclusion criteria

Patients must meet all of the following inclusion criteria to be eligible for inclusion in the study:

090177e19b7d94e0\Approved\Approved On: 29-Aug-2023 01:40 (GMT)

Apixaban

B0661183 NON-INTERVENTIONAL STUDY PROTOCOL

Protocol Version: 2.0 29 July 2022

1. Patients with ≥ 1 diagnosis code for VTE (inpatient [primary or secondary discharge diagnosis] or any position on an outpatient non-ancillary medical claim) between January 1, 2017 and October 31, 2021 (selection window).
 - Note: Qualifying outpatient encounters followed by qualifying inpatient encounters within 7 days will be considered an inpatient VTE event, unless LMWH or apixaban was initiated between encounters, in which case it will be classified as an outpatient VTE event
 - First date of claim with a VTE diagnosis code will be termed the ‘index VTE encounter’

2. Evidence of having active cancer, defined as ≥ 2 medical claims with a cancer diagnosis (excluding nonmelanoma skin cancer) on different days during the 6 months before or within 30-days after the index VTE event

OR

≥ 1 medical claim for a cancer diagnosis AND ≥ 1 claim for cancer treatment (eg: chemotherapy, radiation, immunotherapy, hormone therapy or cancer related surgery using national drug codes (NDC), international classification of diseases, tenth revision, clinical modification [ICD-10-CM] procedure codes or healthcare common procedure coding system [HCPCS] codes) during 6 months before or within 30 days after the index VTE encounter

3. ≥ 1 claim of apixaban or LMWH (dalteparin orenoxaparin) on or within 30 days following the index VTE encounter.
 - a. The date of the first apixaban or LMWH prescription fill will be designated as the index date
4. ≥ 12 months of continuous enrollment prior to the index date (pre-index)
5. ≥ 1 months of continuous enrollment including and following the index date (post-index)
 - a. Note: Each patient will have a variable follow-up period with a minimum of 1-month follow-up. Patients will be followed from the day after the index date through the earliest of the following: health plan disenrollment, index therapy discontinuation, switch to another anticoagulant, or study end (December 31, 2021).
 - b. Discontinuation will be defined as occurrence of a ≥ 30 day gap from the run-out of days’ supply of the index LMWH or apixaban prescription. The date of the discontinuation will be defined as the last day of the days’ supply of the last filled prescription.

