9.1.2. Exclusion criteria

Patients meeting any of the following criteria will be excluded from the study:

1. ≥ 1 claim with a ICD-10 diagnosis code of atrial fibrillation/flutter during the 12-month pre-index
2. ≥ 1 claim with a ICD-10 procedure code of mechanical heart valve during the 12-month pre-index
3. ≥ 1 claim with a ICD-10 diagnosis code of VTE diagnosis during the 12-month prior to index VTE encounter
4. ≥ 1 prescription claim of OAC or parenteral anticoagulant (PAC) (unless prophylactic) before the index VTE encounter
 - a. The OAC or PAC prescription claim will be considered prophylactic if duration of the prescription is ≤ 42 days AND the start date of OAC or PAC occurs within 2 days before or 7 days after knee/hip replacement surgery
OR
Start date of OAC or PAC occurred within 7 days after the admission of an hospitalization associated with 'medically ill' (primary discharge diagnosis; codes provided separately) AND with a ≥ 3 -day length of stay of the hospitalization
5. ≥ 1 claim with a ICD-10 procedure code or Common Procedural Terminology (CPT) code of inferior vena cava filter during the study period
6. ≥ 1 claim with a ICD-10 diagnosis code of antiphospholipid syndrome (APS) during the study period
7. ≥ 1 claim with a ICD-10 diagnosis code or procedure code (ICD-10 or HCPCS codes) of pregnancy during the study period
8. ≥ 1 prescription claim of an anticoagulant other than index apixaban or LMWH treatment between the index VTE encounter and index date. Other anticoagulants include heparin, fondaparinux, warfarin, dabigatran, rivaroxaban, and edoxaban
9. Data quality issues (with Medicare Cost coverage or State Children's Health Insurance Program (SCHIP), invalid year of birth or health plan enrollment dates) ('missing' will be reported for gender and region)

PFIZER CONFIDENTIAL

CT24-WI-GL02-RF02 4.0 Non-Interventional Study Protocol Template For Secondary Data Collection Study 01-Jun-2022

Page 18 of 35

090177e19b7d94e0\Approved\Approved On: 29-Aug-2023 01:40 (GMT)

Apixaban**B0661183 NON-INTERVENTIONAL STUDY PROTOCOL**

Protocol Version: 2.0 29 July 2022

A preliminary attrition table will be provided to Pfizer/Bristol Myers Squibb (BMS) for review, at which time modifications to the inclusion and exclusion criteria may be implemented.

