090177e19b7d94e0\Approved\Approved On: 29-Aug-2023 01:40 (GMT)

PFIZER CONFIDENTIAL

CT24-WI-GL02-RF02 4.0 Non-Interventional Study Protocol Template For Secondary Data Collection Study 01-Jun-2022

Page 22 of 35

Apixaban

B0661183 NON-INTERVENTIONAL STUDY PROTOCOL

Protocol Version: 2.0 29 July 2022

- Cancer type (n, %)
 - Hematologic cancers
 - Leukemia
 - Lymphoma
 - Multiple myeloma
 - Non-hematologic cancers
- Cancer related treatments (n, %)
 - Chemotherapy
 - Hormone therapy
 - Immunotherapy
 - Radiation
 - Cancer related surgery
- Modified VTE Khorana Risk Scale¹⁰ (n, %)
 - Very high risk (brain, stomach, and pancreas)
 - High risk (lung, lymphoma, gynecologic, bladder, testicular and renal cell carcinoma)
 - Other cancers

Baseline HCRU and costs

- Patients with a pre-index hospitalization (n, %)
- Patients with a pre-index emergency room (ER) visit (n, %)
- Patients with a pre-index outpatient physician office visit (n, %)
 - Number of pre-index outpatient physician office visits (mean, SD, median, IQR)
- Total all-cause healthcare costs (mean, SD median, IQR)
 - Inpatient
 - Outpatient medical
 - ER
 - Pharmacy

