ANNEX 1. LIST OF STAND-ALONE DOCUMENTS

Table shells will be provided in a separate file.

Codes used in this study are provided in separate files. Categories include:

- VTE and cancer diagnosis
- Diagnosis codes of interest
- Comorbidities of interest
- Medications of interest
- Procedures of interest
- Major bleeding and CRNM bleeding diagnosis

Number	Document reference number	Date	Title
1		16 June 2022	IQVIA Pfizer Apixaban LMWH_Final Table Shells_20220616

Apixaban
B0661183 NON-INTERVENTIONAL STUDY PROTOCOL
Protocol Version: 2.0 29 July 2022

2		16 June 2022	VTE Cancer study Codes
---	--	--------------	------------------------

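### Nonmelanoma skin cancer is excluded from only one of the two routes to active cancer, so the criterion as written can admit patients whom the first route turns away

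*Combined protocol and SAP*

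**What the plan says.** Section 9.1.1, criterion 2, defines active cancer by two routes joined by OR. Both look at the 6 months before and the 30 days after the index VTE.

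- Route 1 asks for "≥ 2 medical claims with a cancer diagnosis (excluding nonmelanoma skin cancer) on different days".
- Route 2 asks for "≥ 1 medical claim for a cancer diagnosis AND ≥ 1 claim for cancer treatment". Its examples of treatment are "chemotherapy, radiation, immunotherapy, hormone therapy or cancer related surgery", with no limit by type of cancer.

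The NMSC exclusion stands in route 1 only. Section 9.1.2 opens with "Patients meeting any of the following criteria will be excluded from the study" and lists nine criteria, none of which concerns NMSC or cancer type. NMSC is mentioned nowhere else in the supplied text.

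In section 9.3.1 the cancer-site list has no skin or residual category. An NMSC-only patient could be classed only as non-hematologic and, on the modified Khorana scale, as "Other cancers". Annex 1 says "Codes used in this study are provided in separate files". Those files were not available for this review.

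**The concern.** The exclusion in route 1 shows that the sponsor does not regard NMSC alone as active cancer. An alternative route without the same exclusion can undo it. A patient with many NMSC claims and no other cancer fails route 1, yet meets route 2 with one of those claims plus a radiation or surgery claim that counts as cancer treatment.

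Two things are at stake. The first is the population: the study is meant to describe VTE in patients with active cancer, and NMSC-only patients would blur that even if they were spread evenly over the cohorts. The second is the comparison of all-cause and event-related costs, which are the primary objectives. If NMSC-only patients differ in cost from the rest, and if their share differs between the cohorts after weighting, the cost ratio moves for a reason unrelated to the drug. No listed covariate identifies these patients directly, and section 9.7 does not name the covariates that enter the weights.

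**Working it through.** **Step 1. The two routes side by side, for an NMSC-only patient.**

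- Route 1, any number of NMSC claims: fails, because NMSC is excluded.
- Route 2, one NMSC claim and no treatment claim: fails.
- Route 2, one NMSC claim and one claim counted as radiation or cancer-related surgery: passes as written.
- The nine exclusion criteria in 9.1.2: none applies on account of NMSC.

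The gap therefore follows from the text alone. Whether it operates depends on the code lists.

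**Step 2. The plan's own figure.** The documents give no number for NMSC. The only related figure is the minimum cohort size in section 9.5, used below for scale. With recurrent VTE rates of 5.6% and 7.9%, two-sided 5% and 80% power, the pooled-variance formula gives

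n = [1.960 × √(2 × 0.0675 × 0.9325) + 0.8416 × √(0.056 × 0.944 + 0.079 × 0.921)]² / 0.023² = 0.9937² / 0.000529 ≈ 1,867.

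The other rates (148/3,393 and 396/6,108) give 1,788. Both stated figures reproduce, and this point does not dispute them.

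**Step 3. Crude effect on the cost ratio, under assumptions.** Let fA and fL be the NMSC-only shares in the apixaban and LMWH cohorts, and k their mean cost relative to other patients. None of these is in the documents. With no true difference,

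ratio = (1 − fA(1 − k)) / (1 − fL(1 − k)).

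- Equal shares: ratio = 1 for any k. Both means fall by the fraction f(1 − k).
- fA = 2%, fL = 0.5%, k = 0.5: 0.9900 / 0.9975 = 0.9925.
- fA = 6%, fL = 2%, k = 0.35: 0.961 / 0.987 = 0.974.
- fA = 10%, fL = 3%, k = 0.2: 0.920 / 0.976 = 0.943.
- Shares swapped between the cohorts: the reciprocals, from 1/0.9925 = 1.008 to 1/0.943 = 1.06.

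A narrower set of assumptions (2% vs 1% up to 5% vs 1%, k from 0.1 to 0.5) gives 0.964 to 0.995. All of these are mixture calculations before any weighting or regression.

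**Step 4. Scale.** At 1,867 per cohort, ignoring the weights, the standard error of the log cost ratio is about CV × √(2/1,867) = CV × 0.0327. That is 4.9%, 6.5% and 8.2% for assumed coefficients of variation of 1.5, 2 and 2.5. At a CV of 2, the three unequal cases amount to about 0.12, 0.41 and 0.90 standard errors (log ratios of −0.0075, −0.027 and −0.059, each divided by 0.0655).

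**The case against.** The strongest reply is that both routes use the same term, cancer diagnosis, and that a parenthesis at first use may be meant to define it for the whole criterion. If the cancer code file omits NMSC, no such patient enters. This stands as a limit: the review cannot show that any NMSC-only patient would be admitted. It does not remove the defect, because the text attaches the exclusion to one route and nothing supplied says that it is built into the term.

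A reader might also infer that route 2 lets back in most of the patients whom route 1 removes. The documents do not support that. They give no counts, and the procedure list is not shown. Route 2 names NDC, ICD-10-CM procedure and HCPCS codes but not CPT, which the protocol names separately elsewhere (exclusion 5 in 9.1.2, baseline bleeds in 9.3.1). HCPCS can be read to include CPT, so this settles nothing, but whether a skin excision counts as cancer surgery is unknown.

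The crude ratios also give no credit for adjustment. Section 9.3 plans IPTW and GLM adjustment, and section 9.3.1 lists baseline cost, hospitalization, prescriber specialty and separate cancer-treatment indicators, which could separate such patients in part. That stands, although use of these variables in the weights is not guaranteed.

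Finally, the missing skin category is weak evidence by itself, since the site list also has no entry for melanoma or renal cancer. It shows only that no site variable picks these patients out.

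**Conclusion.** The inconsistency is real and can be read directly from criterion 2. As written, an NMSC-only patient with a qualifying treatment claim can enter as an active-cancer patient, against the evident intent of route 1. If the code file already omits NMSC for both routes, the fault is one of wording.

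It is tempting to conclude that the gap favors apixaban, on the view that NMSC-only patients are cheap to treat and are mostly given apixaban. Neither premise is in the documents. Equal weighted shares leave the ratio unbiased, and the opposite imbalance reverses the sign. The range of about 0.94-0.99 is a crude illustration on assumed shares and costs, likely to shrink after adjustment. It is not an estimate of bias in the reported result. What can be said is that any such effect would be systematic, so a larger sample would not remove it, and that the match between the stated and the admitted population suffers in any case.

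**What to change.** State at the head of criterion 2 that a cancer diagnosis means any malignancy other than NMSC, for both routes. Confirm that the cancer diagnosis code list agrees, apply the same definition to the cancer-related covariates in section 9.3.1, and show the number removed as a line in the attrition table. Section 9.1.2 already provides for a review of a preliminary attrition table, at which the criteria may be modified.

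A further rule, that surgery or radiation claims linked to NMSC do not count as cancer treatment, is a separate and optional choice. It would also remove patients with another cancer, for example one with a single lung-cancer claim whose only treatment claim is an NMSC excision. It is not needed to make the two routes consistent.

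The cost is one sentence, a check of the code list and a slightly smaller cohort. No new data are needed.

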9.1. Study period and study design

The analysis will be conducted using data from 01 January 2016 through 31 December 2021 or the latest available data at the time of extraction (i.e., the *study period*). Patients will be identified during a *selection window* of 01 January 2017 to 31 October 2021. The date of the first apixaban or LMWH prescription on or within the 30 days following a VTE diagnosis will be termed as the index date. Patients will be required to have continuous enrollment with medical and pharmacy benefits for 12-months prior to the index date to assess study eligibility criteria and to measure baseline characteristics (*the baseline or pre-index period*). Patients will also be required to have continuous enrollment with medical and pharmacy benefits for at least one month (30 days) starting on and following the index date (the follow-up or post-index period) and will be followed through the earliest of the following: health plan disenrollment, index therapy discontinuation, switch to another anticoagulant (includes switch to the other study medication or unfractionated heparin, fondaparinux, warfarin, rivaroxaban, dabigatran, or edoxaban), or end of study period (31 December 2021).

Note: Patients in the LMWH cohort will NOT be considered to have discontinued or switched if they change to an LMWH other than the index LMWH (dalteparin, enoxaparin, or tinzaparin).

Figure 1. Study Period

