9.2. Cohorts

From the overall cohort of VTE patients with cancer, two cohorts of interest will be created based on the type of anticoagulation treatment received within 30 days following the index VTE encounter date.

- **Cohort #1** – Apixaban: Evidence of apixaban use (and no other anticoagulant [LMWH, other OAC, heparin or fondaparinux] between the index VTE encounter date and index date).
- **Cohort #2** – LMWH: Evidence of LMWH use (and no apixaban or other anticoagulant between the VTE index date and LMWH initiation date).

LMWH should be used for at least 14 days to ensure that LMWH was not intended for short-term bridge therapy.

Analyses will be stratified by these two cohorts, as defined in section 8.3.1-8.3.3.

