9.4. Data sources

This study will utilize data from IQVIA's PharMetrics® Plus. IQVIA's collaboration with Health Intelligence Company, which operates as Blue Health Intelligence, allows IQVIA's bio-pharmaceutical clients sole access to one of the largest United States (US) health plan claims databases and adds IQVIA's market leading health plan claims database. The aggregated database comprises adjudicated claims for more than 190 million unique enrollees across the US. Enrollees with both medical and pharmacy coverage in 2020 represented 40 million lives. Data are available from 2010 onwards, with a typical 4- to 6-month lag due to claims adjudication.

PharMetrics Plus has diverse representation of geography, employers, payers, providers and therapy areas. Patients in each zip code and every Metropolitan Statistical Area of the US are included, with coverage of data from 90% of US hospitals, 80% of all US doctors, and representation from 85% of the Fortune 100 companies. In addition to standard fields such as inpatient and outpatient diagnosis and procedures, retail and mail-order prescription records, PharMetrics Plus has detailed information on the pharmacy and medical benefit (copayment, deductible), the inpatient stay (admission type and source, discharge status) and provider details (specialty, provider identifier [ID]). All zip codes in the US are covered and reported allowing more granular patient segmentation and comparisons by geography. Payment amounts include the negotiated rate between the plan and providers (allowed) and the actual amount paid by health plans to the provider for all services rendered. Charge amount is also available for a subset of claims. Other data elements include dates of service, demographic

PFIZER CONFIDENTIAL

CT24-WI-GL02-RF02 4.0 Non-Interventional Study Protocol Template For Secondary Data Collection Study 01-Jun-2022

Page 27 of 35

090177e19b7d94e0\Approved\Approved On: 29-Aug-2023 01:40 (GMT)

Apixaban

B0661183 NON-INTERVENTIONAL STUDY PROTOCOL

Protocol Version: 2.0 29 July 2022

variables (age, gender, and geographic region), product type (e.g., HMO, PPO), payer type (e.g., commercial, self-insured), and start and stop dates of health-plan enrollment.

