9.9. Limitations of the research methods

While claims data are valuable for the efficient and effective examination of healthcare outcomes, treatment patterns, HCRU, and costs, all claims databases have certain inherent limitations affecting generalizability because the claims are collected for the purpose of payment within the commercially-insured population and not research. Results and conclusions are limited to the patient population, which consisted of patients enrolled in managed care plans, and may not be generalizable to other or non-commercially-insured populations in the US. These limitations do not significantly reduce the strength of this study and its results, but they must be considered during interpretation.

Presence of a diagnosis code on a medical encounter or outside claim may have not been conclusive of positive presence of disease, as the diagnosis code may have been incorrectly coded or included as rule-out criteria rather than actual disease. This risk may be minimal in this study. Presence of a claim for a dispensed medication does not indicate that the medication was consumed or that it was taken as prescribed. Medications provided as samples by the physician are not observable in the pharmacy data.

Only patients with a continuous eligibility were included, and thus patients who did not maintain membership for at least 13 months (i.e., 12 months prior to and 1-month following the index date) were not included in the sample.

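### Cohort entry depends on 30 days of enrollment after treatment starts, with no provision for death, so early exits and their costs are left out; an all-initiator analysis should be added beside the planned one

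*Combined protocol and SAP*

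**What the plan says.** Criterion 5 in section 9.1.1 requires "≥ 1 months of continuous enrollment including and following the index date (post-index". Section 9.1 gives the length, with medical and pharmacy benefits: "for at least one month (30 days) starting on and following the index date". The rule covers both cohorts and makes no exception for a patient who dies.

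Follow-up ends at the earliest of "health plan disenrollment, index therapy discontinuation, switch to another anticoagulant, or study end (December 31, 2021". Death is not in this list, nor in the matching lists in the abstract and section 9.1, and it is not an outcome.

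Section 9.9 acknowledges that "patients who did not maintain membership for at least 13 months" were left out. It does not mention death, a direction of bias or a possible difference between cohorts. The protocol text plans no analysis without the requirement; the table shells are a separate file. Section 9.4 says the data describe "the inpatient stay (admission type and source, discharge status", so a death in hospital can in principle be seen.

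Section 9.2 adds a second post-index condition, for one cohort only: "LMWH should be used for at least 14 days to ensure that LMWH was not intended for short-term bridge therapy".

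**The concern.** Whether a patient stays enrolled for 30 days is known only after treatment has begun. The population has active cancer and a new VTE, so death is a plausible reason for enrollment to stop in the first month. Take a patient admitted with a fatal major bleed on day 12 whose coverage then ends. That patient is excluded, and so is the admission. Yet section 9.3.3 counts exactly such an admission as a major bleeding event, and its cost belongs to a primary objective (section 8).

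Two things are at stake. The first is the level of cost: means describe only those enrolled at 30 days. The second is the comparison: if entry depends on something that treatment changes, the cohorts are no longer comparable even when baseline characteristics are balanced. Weights fitted in the retained patients cannot bring the others back.

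**Working it through.** **1. The plan's own figures.** The documents give no rate of death or disenrollment in the first month and no cost for such patients, so there is no figure on this point to reproduce. The one related calculation is the sample size for recurrent VTE (section 9.5). The two-proportion formula with pooled variance is n = [1.960·√(2p̄(1−p̄)) + 0.842·√(p₁(1−p₁)+p₂(1−p₂))]² / (p₁−p₂)². It gives 1,867 for 5.6% vs 7.9% (stated 1,867) and 1,789 for 4.362% vs 6.483% (stated 1,788). Keeping 1,867 after losing 2%, 5% or 10% needs 1,867/0.98 = 1,906, 1,867/0.95 = 1,966 or 1,867/0.90 = 2,075 initiators. The feasibility count for apixaban, before other criteria, is 4,972. The issue is bias rather than size.

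**2. Is the rule needed to secure follow-up time?** The qualifying VTE falls "between January 1, 2017 and October 31, 2021 (selection window", and the index fill comes within 30 days, so by 30 November 2021. Thirty days counted from then end on 29 December 2021, before study end on 31 December. The calendar excludes nobody; the rule removes only patients whose enrollment stops.

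Nor does the rule secure the stated minimum: "Each patient will have a variable follow-up period with a minimum of 1-month follow-up". Discontinuation is dated to the last day of supply, so an enrolled patient with a single 14-day fill and no refill has about 14 days.

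**3. Size under assumed values.** Let e_A and e_L be the shares excluded in the apixaban and LMWH cohorts, and m the mean cost of an excluded patient relative to a retained one. Suppose retained patients cost the same in both cohorts, so the observed ratio is 1.00. With everyone kept, the LMWH/apixaban ratio is (1−e_L+m·e_L)/(1−e_A+m·e_A).

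| e_A, e_L | m = 2 | m = 3 | m = 5 |
|---|---|---|---|
| 2%, 5% | 1.03 | 1.06 | 1.11 |
| 5%, 10% | 1.05 | 1.09 | 1.17 |
| 5%, 5% | 1.00 | 1.00 | 1.00 |

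For 5% and 10% at m = 3: (0.90+0.30)/(0.95+0.15) = 1.20/1.10 = 1.09. With 5% in both, means are understated by 1−1/1.10 = 9% (m = 3) or 1−1/1.20 = 17% (m = 5). All values of e and m are assumptions, as is which cohort loses more.

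**4. What weighting does and does not repair.** Assume 30% of patients are severe. LMWH goes to 70% of severe and 50% of other patients. Thirty-day exit is 12% vs 2%, relative cost 2 vs 1, and exit multiplies cost by 4. The severe share is then 0.21/0.56 = 37.5% in LMWH and 0.09/0.44 = 20.5% in apixaban, and exit is 5.75% vs 4.05%. Mean cost with everyone kept is 2×(0.88+0.48) = 2.72 for severe and 0.98+0.08 = 1.06 for other patients.

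- Severity measured and weighted, no drug effect: ratio 1.00 with or without the rule.
- Severity measured, LMWH raises exit 1.5-fold: severe LMWH patients cost 2×(0.82+0.72) = 3.08, others 0.97+0.12 = 1.09. All initiators: (0.3×3.08+0.7×1.09)/(0.3×2.72+0.7×1.06) = 1.687/1.558 = 1.08. Retained patients: 1.00. The rule hides the effect.
- Severity unmeasured, no drug effect (true ratio 1.00): all initiators 1.6825/1.3995 = 1.20. In retained patients the severe shares become 35.0% and 18.8%, giving 1.350/1.188 = 1.14. Here the rule moves the estimate towards the truth.

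So unequal exit alone does not bias the weighted comparison. A treatment effect on exit does. Unmeasured severity leaves a bias whose change under the rule can go either way.

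**The case against.** **Death and enrollment.** Section 9.4 lists enrollment start and stop dates and discharge status, but nothing says that death stops enrollment or how quickly. If the enrollment record outlasts the death, the patient stays in. A reader might infer that the rule demonstrably removes the costliest patients. The documents do not show that, and costly early events in patients who remain enrolled are kept. This objection stands, so the point has to be conditional.

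**Channeling.** A reader might infer that giving one drug to sicker patients is enough to bias the result. Weighting is planned (section 9.7), and section 9.3.1 lists cancer site, cancer treatment, a VTE risk scale, comorbidity indices and baseline cost. Step 4 shows that measured severity can be handled. What remains is that section 9.7 does not name the covariates in the weights, and section 9.3.1 lists no stage, metastatic status or performance status.

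**Magnitude.** Step 3 uses crude means with assumed inputs, whereas the plan compares weighted per-patient monthly cost over variable follow-up. Reading 1.09 as the distortion in the planned estimate is not supported.

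**A purpose for the rule.** Dividing by days and multiplying by 30 turns three days of follow-up into a tenfold cost, so a minimum enrollment has a stabilizing role. That is fair, but by step 2 the rule does not prevent short follow-up, and another estimator removes the problem.

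**Disclosure.** Section 9.9 states the exclusion, and section 9.1.2 provides an attrition table and lets criteria change after its review. This is disclosure without an analysis, but it makes the remedy cheap.

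**Conclusion.** The point holds in conditional form. Eligibility rests on enrollment after treatment start, death is nowhere provided for, and the calendar does not require the rule. If early death ends enrollment, those patients leave with their costs. Means are then too low if they cost more than retained patients. The comparison is biased if treatment affects early exit or if severity outside the weights drives it.

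A drug effect on fatal early events is not far-fetched for this plan: section 7 says apixaban lowers recurrent VTE and major bleeding, and section 9.5 assumes different recurrence rates. The documents still give no early mortality, so size and direction stay open. The 3% to 17% range and the 9% to 17% understatement illustrate assumed inputs and are not estimates.

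A reader might go further and ask for criterion 5 simply to be deleted. The material does not support that. With unmeasured severity the all-initiator result can lie further from the truth, and deletion alone would leave the LMWH-only 14-day condition acting on one cohort. Showing both results is the defensible step.

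**What to change.** 1. Add an analysis of all initiators who meet the other criteria, without the 30-day enrollment requirement. Follow each from index to the existing end points plus observed death, taken from inpatient discharge status. Waiving the rule only for patients discharged as dead would select on outcome and should be avoided.
2. In that analysis, estimate cost as IPTW-weighted total cost over weighted total person-time, or over a fixed window with censoring weights, with the weights refitted in all initiators. Taking observed cost as the full first month for everyone with short follow-up would count unseen days of administrative exits as zero.
3. Apply the 14-day LMWH condition of section 9.2 so that it cannot remove early deaths from one cohort only, for example by days' supply dispensed at index.
4. In the attrition table of section 9.1.2, report the number removed by criterion 5 by cohort, and by reason where known.
5. Present the 30-day-enrolled and all-initiator results side by side. If they differ, limit the conclusion to patients enrolled at 30 days, and say so in section 9.9.

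The cost is protocol wording and one more cohort build. Some patients will enter with short administrative follow-up, and deaths outside hospital will still appear only as disenrollment.
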